### 1.1.2 Screening for Low Gastric Acid Secretor

Electrical impedance Tomography (EIT) method that produces qualitative estimates of gastric acid secretion will be used for screening low gastric acid secretor.

#### Electrical Impedance Tomography (EIT)

The Electrical Impedance Tomography (EIT) method has been described in detail earlier (Brown et al. 1985, Avill et al. 1987, Mangnall et al. 1987, Baxter et al. 1988). The principal of the test is that secretions of H+ ion (acid) into the stomach alters the ionic conductivity, which can generate tomographic image and can be measured, like computer scan. The system and software were developed at the Institute for Biomedical Equipment Evaluation and Service in Sheffield, UK. The system includes a data collection unit to measure and process the signals received from electrodes placed on the body surface, and a microcomputer to reconstruct the EIT image. It uses 16 measuring electrodes plus a common electrode for noise rejection, and it operates with a current of 1mA at 50kHz. By applying more than 2 electrodes, the resistivity can be measured between any pair of electrodes, and a tomographic picture of resistivity (resistance per length) in the body can be produced. With a 16-electrode array, 208 measurements are made during each cycle of 100 ms. Several cycles are added together to form a data set. Electrode contact is monitored by reference to an oscilloscope. The total test time is 2 hours.

Gastric resistivity is measured through 16 electrodes separately placed at equal distance in a horizontal plane around the abdomen at the level of the eighth costal cartilage (5 cm above the umbilicus), a plane transecting the gastric fundus. The common electrode is placed in the left lower back. Following an initial reference image, 3-minute frames are obtained for 120 min. Subsequent data sets are then back-projected against the initial set to produce a cross-sectional image of the change in distribution of resistivity in the area of the electrodes. After 30 min., 6µ/kg body weight pentagastrin (Cambridge Laboratories, Newcastle upon Tyne, UK) is injected subcutaneously. EIT images are then obtained for 90 min. After 120 min., the subject is given 250 ml normal saline as a drink in order to visualize the position of the stomach. A fixed size of the gastric region of interest (ROI) is outlined from the image obtained immediately after ingestion of the drink. The ROI thus allows comparison of actual resistivity changes during the

Principal Investigator (Last, first, middle): [name]

examination. The changes in logarithms of impedance over time within ROI are measured and plotted. Values for total gastric acid output are expressed as Area under Curve (AUC) calculated from the graph using a standard formula (Thompson et al. 1972). The change of resistivity after pentagastrin stimulation is calculated by subtracting the actual baseline AUC value extrapolated for 90 min, basal AUC, from that of the stimulated AUC. The technique was recently validated ([name] et al. 1997a). The AUC value <300 will be considered indication of hypochlorhydria. The equipment is not available at ICDDR,B and thus needs to be purchased.

The manufacturer of the EIT system now markets the portable version of the system. Therefore, we also plan to validate the portable system of EIT against the standard gastric intubation test in additional 40 women prior to screening for *H. pylori* infection.

### 1.1.3 Validation of Portable EIT System

Before application in the field, the portable EIT system will be validated against the standard intubation (Pentagastrin) test. Gastric intubation and EIT measurement will be performed on 40 women at two separate, randomly chosen occasions.

#### Gastric Intubation

After an overnight fast, a soft nasogastric tube will be introduced, and the tip of the tube will be positioned at the most dependent part of the stomach under fluoroscopic control. After aspirating resting gastric juice, basal samples will be collected for 30 minutes. Pentagastrin (Cambridge Laboratories, Newcastle upon Tyne, UK) will be administered (6 $\mu$ g/kg of body weight) subcutaneously and 15-minute cycles of aspiration of gastric juice will continue for an additional 90 minutes. Acidity of each sample will be measured by titration of 1.0 ml gastric juice with 0.01N sodium hydroxide to pH 7.4 using an automatic titrator (Metrohm, Herisau, Switzerland). Total acid output will be calculated for each time point by multiplying volume of gastric juice and acid concentration. Acid outputs/hour will be calculated based on 4 baseline samples (basal acid output) and the 4 first samples collected after administration of pentagastrin (stimulated acid output).

Adverse events related to Injection of 6 $\mu$ g/kg pentagastrin are extremely rare. However, there may be transient hypotension, nausea, light headedness, malaise, tachycardia, flushing, and rash; all rapidly responding to intravenous antihistamine, and hydrocortisone. We will use hydrocortisone 5 mg/kg dose, and/or chlorpheniramine maleate 2 mg/dose to manage the events.

The validation of EIT system against standard intubation test will be performed in two ways, as done before by [name] et al 1995 . Firstly, in term of overall correlation between gastric acid output and AUC in EIT system. Second, in term of sensitivity and specificity of EIT system as compared to the standard intubation test. AUC below 300, and total stimulated gastric acid below 10 mmol/h will be considered indicative of hypochlorhydria. A dose-response curve analysing the basal phase and with pentagastrin at different dose (1  $\mu$ g/kg, 3  $\mu$ g/kg, and 6  $\mu$ g/kg) will also be performed.

Principal Investigator (Last, first, middle): [name]

### 1.1.4 Screening for Iron Deficiency Anaemia (IDA)

Venous blood samples (2.5 ml) will be collected in EDTA-treated tubes, and analyzed for Fe status parameters- hemoglobin (Hb), serum ferritin (SF), serum transferrin receptor (sTfR), and serum iron and iron binding capacity (TIBC).

#### 1.1.4.1 Laboratory Diagnosis of Iron Deficiency Anemia

Measurement of Hb concentration is the most useful for screening test for IDA since it directly reflects the quantity of the most abundant essential iron compound in the body. However, the diagnosis of IDA requires estimation of SF concentration ( Linpisarn et al 1996), and sTfR (Cook et al 1993) due to the fact that Hb concentration may be transiently depressed in inflammation or infection, and thus does not indicate pathological anemia under such circumstances. Of all the biochemical tests for assessing Fe status, a low SF is the most specific test for iron deficiency. However, the major disadvantage of SF is its readily elevation in response to infection or inflammatory conditions. The impact of infection on SF is often described as a “reticuloendothelial block” , which reduces the release of Fe from phagocytic cells breaking down Hb, and thus reduce the serum Fe concentrations by intracellular accumulation of ferritin iron (Means & Krantz 1992).

Determination of sTfR is a promising new test for evaluation of Fe status. A major advantage of sTfR is that unlike SF infection, or inflammatory process does not significantly influence it. However, sTfR levels are increased under conditions of increased breakdown of RBC e.g. in hemolytic anemia such as thalassaemia. A uniform cutoff value of >8.5 mg/L is regarded as elevation of sTfR, and thus of IDA or hemolytic anemia. When performed in conjunction with SF measurements, the sTfR serves to distinguish true IDA from anaemia of chronic disease or inflammatory diseases, and thus offers a major advantage in determining true prevalence of IDA in population studies (Cook et al 1993).

Transferrin saturation (serum iron/iron binding capacity) is the most widely available confirmatory tests for iron deficiency. Typically serum iron is depressed and the iron binding capacity is elevated in iron deficiency, but the later is not consistent finding and its absence by no means excludes the diagnosis. Low transferrin saturation and serum irons are characteristics of both iron deficiency, or recent or concurrent infection.

The following table indicates the indicators of iron deficiency and iron deficiency anemia.

**Table: Laboratory indicators of iron deficiency and iron deficiency anaemia**

Indicators	Iron deficiency	Iron deficiency anemia
Hb	↔	↓
SF	↓	↓
sTfR	↑	↑

### 1.1.4.2. Definition of iron deficiency anaemia

Iron deficiency anaemia will be defined as: haemoglobin value below the WHO cut-off for women (12 g/dL) (Dallman et al 1995) plus two out of three abnormal Fe status measurements; plasma ferritin values <12 g/L, plasma circulating transferrin receptor values >8.5 mg/L (Cook et al 1993) and transferrin saturation values <15%.

### 1.1.5 Sample Size

#### *Prevalence of HP-linked IDA and Hypochlorhydria*

The reported prevalence rate of *Helicobacter pylori* infection in the community is 80%. We assume 60% of the Hp-infected women will have hypochlorhydria and 70% of the Hp-infected hypochlorhydric women will have iron deficiency anaemia. However, we like to have an estimate of the prevalence of Hp infection plus hypochlorhydria plus iron deficiency anaemia to be corrected within  $\pm 5.0\%$  with 95% confidence

The required sample size will be:

$$\frac{\epsilon}{\sqrt{PQ/n}} = Z_{\alpha}$$

Where  $\epsilon$  = allowable error  
P = estimated prevalence  
Q = 1-P  
n = the required sample size  
 $Z_{\alpha}$  = value of the normal variation for (1- $\alpha$ )% confidence

Assuming:

$$\epsilon = 7.5\%$$

$$P = 0.8 * 0.6 * 0.7 \\ \cong 34\%$$

$$Q = 1-P = 66\%$$

$$\text{and } Z_{\alpha} = 1.96 \text{ (95\% confidence)}$$

The required sample size of Hp infected women with hypochlorhydria and IDA:

$$\frac{\epsilon}{\sqrt{PQ/n}} = Z_{\alpha}$$

$$\frac{0.075}{\sqrt{0.34 * 0.66/n}} = 1.96$$

Therefore  $n = 1.96^2 * 0.34 * 0.66 / 0.075^2$   
= 154 women. However, we will take 160 sample.

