### 1. Part 1: First Objective of the Study

**To determine the prevalence of *H. pylori* infection, low gastric acid secretion, and iron deficiency anaemia in Bangladeshi women in the reproductive age living in a peri-urban slum of Dhaka city.**

One hundred sixty (160) adult women aged, 20-40 years, living in Nandipara, a peri-urban community of Dhaka city will be screened for *H. pylori* infection using the  $^{13}\text{C}$ -urea breath test. Their gastric acid secretion will be assessed by the non-invasive, Electrical Impedance Tomography ([name] et al. 1997); and their body iron status will be determined. All subjects will be fully informed about the aims of the study and the procedures to be followed, and written informed consent will be obtained before their enrollment in the study.

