### 2.3 Sample size

The sample size is determined with the assumptions that anaemia will be corrected in 95% women with Anti-Hp therapy plus iron-therapy, while iron therapy alone will correct anaemia in 60% of the women. Thus, the worthwhile difference (D) in correction of anemia will be:

$$D = 95 - 60 = 35\%$$

At 5% level of significance (type I error of 5%) with 80% power (type II error of 20%), and to detect a 35% difference in the outcome (correction of anaemia), the sample size has been estimated as follows:

$$n = 2 P(1-P) * (Z_{\alpha/2} + Z_{\beta})^2 / D^2$$

Where:  $P = (P_1 + P_2) / 2 = (95 + 60) / 2 = 77.5 \%$   
(  $P_1$  is 95% and  $P_2$  is 60% )

$$\begin{aligned} n &= 2 * 0.775 (1-0.775) * (1.96 + 0.86)^2 / (0.35)^2 \\ &= 1.55 * 0.225 * (2.82)^2 / 0.1225 \\ &= 0.34875 * 7.95 / 0.1225 \\ &= 22.6 \\ &\cong 23 \text{ subjects in each of the five groups} \end{aligned}$$

Based on previous study in the same community, we anticipate a drop out rate of approximately 10%. Therefore, the number of women to be enrolled is 25 in each group i.e.  $25 * 5 = 125$  women in total in 5 groups.

The reported prevalence of Hp infection is 80%. We estimate 60 % of infected population will be hypochlorhydric. of whom 70% will have IDA. We need to screen 298 ( $100 / 0.8 * 0.6 * 0.7$ ) women to identify 100 infected women (for four groups) with hypochlorhydria and iron deficiency anemia. As 160 women will be enrolled under the first part of the study we will require 138 ( $298 - 160 = 138$ ) additional women to be screened under the second part of the study.

We need a fifth group of 25 women with Hp infection but without hypochlorhydria. They will be selected from among these 260 women.

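### Section 1.1.5 promises the joint prevalence within ±5.0% but sizes the survey for ±7.5%; 160 women give about ±7.3 points

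*Protocol*

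**What the plan says.** Part 1 of the H. pylori protocol is a prevalence survey. Its size is fixed in the design text ("One hundred sixty (160) adult women aged, 20-40 years, living in Nandipara") and justified only in section 1.1.5, Sample Size.

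That section assumes 80% of women in the community are infected, then states "We assume 60% of the Hp-infected women will have hypochlorhydria". For anaemia, its supposition is that "70% of the Hp-infected hypochlorhydric women will have iron deficiency anaemia". The product of the three rates, rounded to 34%, is the expected joint prevalence of infection, low gastric acid and iron deficiency anaemia (IDA).

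The precision wanted, ±5.0% at the 95% level, is given in prose, in the sentence that contains "we like to have an estimate of the prevalence of Hp infection plus hypochlorhydria plus iron deficiency anaemia to be corrected within". In the list of assumptions that follows, the allowable error is 7.5%. It appears as 0.075 in the worked fraction and again in the final formula. The result is given as "154 women. However, we will take 160 sample".

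**The concern.** One section gives two values for the same design quantity. The sentence stating the goal says ±5.0%, the calculation meant to meet that goal uses 7.5%, and no text links them. Precision is the only criterion offered for the size of Part 1, so the stated criterion is not the one the sample was built on.

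A reader or ethics committee relying on the prose would expect a 95% interval of about 29% to 39% around the assumed 34%. The design would give one about half as wide again.

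**Working it through.** **Inputs, all from section 1.1.5 unless noted.** Infection 80%; low acid among the infected 60%; IDA among those 70%; z = 1.96; stated precision 5.0%; allowable error used 7.5%; 154 women computed, 160 taken. From Facilities Available: about 750 women of reproductive age in the community.

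**Expected joint prevalence.** P = 0.8 × 0.6 × 0.7 = 0.336, rounded in the protocol to 0.34. PQ = 0.34 × 0.66 = 0.2244.

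**The protocol's own figure.** n = z²PQ/ε² = 1.96² × 0.2244 / 0.075² = 0.8621 / 0.005625 = 153.3, so 154. It reproduces.

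**The same formula at the stated precision.** n = 0.8621 / 0.05² = 0.8621 / 0.0025 = 344.8, so 345. That is 345/160 = 2.2 times the planned sample.

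**What 160 women give.** Half-width = 1.96 × √(0.2244/160) = 0.0734, or 7.3 points (26.7% to 41.3%). The ratio to the promise is 7.34/5.0 = 1.47. Put the other way, ±5.0 points is 0.05/√(0.2244/160) = 1.335 standard errors, which is about 82% confidence, not 95%.

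**Readings that might reconcile the figures.**

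| Reading at ±5.0% | Women needed |
|---|---|
| P = 0.34, 95% confidence | 345 |
| Unrounded P = 0.336 | 343 |
| 90% confidence (z = 1.645) | 243 |
| Finite-population correction, N = 750: 344.8/(1 + 343.8/750) | 237 |
| 5% read as relative error (0.05 × 34 = 1.7 points): 0.8621/0.017² | about 2,980 |

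None gives 154 or 160. With the correction for N = 750, 160 women give 0.0734 × √(590/749) = 0.065, or ±6.5 points. Without it, 160 women reach ±5.0 points only if the joint prevalence is about 12% or lower (or 88% or higher).

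**Precision for the quantity named in specific aim 1.** That aim concerns infected women. Expected number infected: 0.8 × 160 = 128. Expected proportion with low acid and IDA: 0.6 × 0.7 = 0.42. Half-width = 1.96 × √(0.42 × 0.58/128) = 0.0855, or about 8.6 points.

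**The case against.** The best defence is that this is a slip in one introductory figure. The 7.5% is used consistently through the calculation, the multiplication is right for it, and 160 is carried consistently through the summary, the design text and section 2.3. That stands, and it is why the point is moderate.

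A second defence is that the community is small. Taking 345 of about 750 women would be 46% of them, and a finite-population correction would be reasonable if the target is this community alone. That has force against quoting 345 without qualification. But the protocol does not use the correction, and with it 160 women still give ±6.5 points. The 750 also counts all women of reproductive age, whereas the survey takes ages 20 to 40, whose number is not given, so the corrected figures rest on an assumption.

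Three stronger readings might be inferred, and the documents do not support them:

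- *That the randomised trial is undersized for the same reason.* Section 2.3 has a separate calculation for correction of anaemia. The precision target plays no part in it.
- *That ±5.0% was promised for specific aim 1.* Section 1.1.5 attaches it to the joint prevalence in all women surveyed. Aim 1 names prevalence among infected women, for which no precision is stated.
- *That the survey could be rescued at no cost by adding the 138 "additional women to be screened under the second part of the study", making 298.* By the protocol's formula that gives 1.96 × √(0.2244/298) = 5.4 points, still short of 5.0; only with the assumed correction would it fall to about 4.2 (0.0538 × √(452/749)). Section 2.3 does not say that every additional woman has all the tests. The exclusions in section 2.4 would also have to be considered, since the acid test uses a pentagastrin injection. The plan as written does not support pooling, and it is not proposed here.

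**Conclusion.** Section 1.1.5 is wrong as written. It states ±5.0% and computes with 7.5%. Under its own formula and P = 34%, the stated precision needs 345 women and the planned 160 deliver ±7.3 points. With an assumed finite-population correction for about 750 women the figures are about 237 and ±6.5, so the promise is missed on either reading.

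These figures rest on the protocol's assumed rates, the normal approximation and simple random sampling. The inconsistency between 5.0% and 7.5% depends on none of them.

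Severity is moderate: a survey precision figure is misstated, but no treatment comparison, power or error rate changes.

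**What to change.** In section 1.1.5, change the stated precision from ±5.0% to ±7.5%, in line with the calculation, and add that 160 women give about ±7.3%. Say that this is the precision of the joint prevalence among all women surveyed. It would help to add that, for the proportion among infected women named in specific aim 1 (about 42% of about 128), the expected half-width is about ±8.6 points.

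The cost is one corrected figure and a sentence, with no change to the sample. If the sponsor does want ±5.0%, the alternative is to enlarge Part 1 to about 345 women, or about 237 if a finite-population correction is adopted and justified in the text.

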## 2. Part 2: Testing of the second objective

### Randomized, double-blind, placebo-controlled, community trial

#### 2.1 Methods

To determine if there is a causal relationship of IDA with Hp infection, or if Hp infection has any relationship with IDA, an intervention study will be conducted on 100 Hp-infected women with hypochlorhydria and IDA. They will be randomized in equal numbers to receive either of the following four interventions:

- (i) Anti Hp therapy: A combination of 500mg clarithromycin twice daily + 500mg amoxicillin twice daily + 40 mg omeprazole once daily for 14 days
- (ii) Anti Hp therapy plus iron: The above + ferrous fumarate containing 60-mg elemental iron each day for 60 days
- (iii) Iron alone: Ferrous fumarate containing 60-mg elemental iron each day for 60 days
- (iv) Placebo: Starch powder

**Fifth group:** There will be a fifth group of 25 women with Hp infection but without hypochlorhydria. This group is required to observe the influence of hypochlorhydria *per se* on IDA. This group will also be treated with Anti-Hp therapy plus iron.

The therapies will be provided in gelatin capsules and will be fed daily in morning and at the evening. The women in the placebo group will receive same amount of starch powder in identical capsules for 60 days. To keep the study blind, all therapies will be kept in identical container and will be fed by a health worker who will remain unaware of the nature of the study and the contents inside the bottles.

The women will be followed for six months after the end of intervention. Hb, SF, and sTfR will be determined at the end of intervention and also, 3 and 6 months after the intervention. Urea breath test will also be performed at the same time. EIT will be repeated 6 months after intervention. The women in the placebo groups will be given anti-Hp therapy plus iron as indicated above at the end of study period of 6 months. Similarly the group (iii) women will also provided anti-Hp therapy at the end of the study. The dose of iron conforms to that used in Bangladesh ( Kolsteren et al 1999).

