*Helicobacter pylori* (Hp) is a major gastrointestinal pathogen that causes gastritis and low gastric acid production. Gastric acid is one of the most important luminal factors necessary for optimal non-haeme iron (Fe) absorption. Thus, low gastric acid is a risk factor for iron deficiency anemia (IDA), which affects millions of people, primarily infants and women in the reproductive age. We hypothesize that poor bioavailability of iron in these countries might be related to low gastric acid output resulting from Hp infection. The frequency of low gastric acid secretor and IDA in such population is not known. We, therefore, propose to investigate the frequency of *H. pylori*-associated low gastric acid secretor (hypochlorhydria) and to evaluate its role in causing IDA in women. One hundred sixty women in the reproductive age, living in Nandipara, a peri-urban community of Dhaka city will be studied to ascertain the frequency of *H. pylori*-associated low acid output and IDA. To investigate the role of Hp in causing hypochlorhydria and IDA, an intervention study is also planned. Four groups (25 in each group) of Hp-infected women with IDA and hypochlorhydria, and another group (fifth group) of 25 women with normochlorhydria will be studied. Hp infected women with IDA and hypochlorhydria will be assigned to one of the four interventions: (i) anti-Hp therapy (triple-therapy with clarithromycin, amoxicillin and omeprazole), (ii) anti-Hp triple therapy plus iron (ferrous fumarate), (iii) iron therapy alone, or (iv) placebo. The fifth group of women with Hp infection and IDA but without hypochlorhydria will be treated with anti-Hp therapy.

Urea breath test will be used for identification of *H. pylori* infection. Iron status will be determined by analyzing hemoglobin, serum ferritin, and circulating transferrin receptor. Electrical Impedance Tomography (EIT) will be used to assess basal and pentagastrin-stimulated gastric acid outputs. Urea breath test, iron status, and EIT will be repeated at the end of intervention, and at 3 and 6 months from the time of initiation of intervention therapy.

This study is expected to provide useful, new information on the role of *H. pylori* infection and hypochlorhydria in the etiology of IDA. The findings of this study, therefore, are likely to influence the design of iron fortification strategies/programmes for reducing the burden and consequences of IDA in the developing countries.

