## 2.5 Laboratory Methods

Hb will be analyzed using the cyanomethemoglobin method (Sigma kit, Sigma, St. Louis, MO). Transferrin saturation will be assessed by analysis of Fe and total Fe-binding capacity (TIBC) (Sigma kit), and plasma ferritin and circulating transferrin receptor will be measured by ELISA (Ramco, Houston, TX). Commercial quality control materials (DiaMed, Cressier sur morat, Switzerland, Sigma and Ramco) will be analyzed together with all series of samples analyzed for Hb, Fe, TIBC and plasma ferritin.

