### 2.6.1 Outcome Measures

- Prevalence of Hp infection and hypochlorhydria before and after intervention
- Prevalence of IDA in each group before and after the intervention
- Rise of serum Hb and SF, transferrin saturation, and reduction in sTfR before and after intervention
- Change of gastric acid output before and after intervention.

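### H. pylori/IDA protocol: the follow-up schedule leaves out transferrin saturation, which both the outcome list and the IDA definition require

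*Protocol*

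**What the plan says.** The point concerns the H. pylori and iron deficiency anaemia (IDA) protocol, which shares a file with a separate child-development protocol.

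- **Definition (1.1.4.2).** IDA is haemoglobin (Hb) below 12 g/dL "plus two out of three abnormal Fe status measurements". The three are ferritin (SF), transferrin receptor (sTfR) and transferrin saturation, the last counted as abnormal below 15%.
- **Screening (1.1.4).** Serum iron and iron-binding capacity (TIBC) are collected with Hb, SF and sTfR, so all three markers exist at entry.
- **Follow-up (2.1).** "Hb, SF, and sTfR will be determined at the end of intervention and also, 3 and 6 months after the intervention". Serum iron and TIBC are not named.
- **Project Summary.** "Iron status will be determined by analyzing hemoglobin, serum ferritin, and circulating transferrin receptor", and iron status is what is to be repeated at follow-up.
- **Outcomes (2.6.1).** "Prevalence of IDA in each group before and after the intervention" and "Rise of serum Hb and SF, transferrin saturation, and reduction in sTfR before and after intervention".
- **Laboratory Methods (2.5).** "Transferrin saturation will be assessed by analysis of Fe and total Fe-binding capacity (TIBC) (Sigma kit"), with no time points.
- **Data Analysis.** Chi-square tests are planned for binary variables, IDA among them, before versus after therapy and between groups. The examples given for continuous change are Hb, SF, sTfR and acid output.

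**The concern.** The visit schedule and the outcome list cannot both be right. A field team working from section 2.1 would not run serum iron or TIBC after treatment. One listed outcome would then have no post-treatment values, and one of the three inputs to the IDA definition would be missing at every follow-up visit. No section says how IDA is to be classified in that case.

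The obvious default is to keep asking for two abnormal markers when only SF and sTfR are available. A woman who entered on low saturation plus one other marker would then stop counting as IDA even if nothing about her iron status had changed. The four randomised arms are made up of women with IDA, so baseline prevalence is 100% on the three-marker rule, and any such reclassification shows up as improvement. At stake are the planned before/after test of IDA and what can be read from the placebo arm. This cannot safely wait for an analysis plan, because an assay not scheduled at the visit may not be recoverable later.

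**Working it through.** **1. The sample size, for reference.** Section 2.3 uses n = 2P(1-P)(1.96+0.86)²/D² with P = 0.775 and D = 0.35. This gives 0.34875 × 7.9524 / 0.1225 = 22.64, so 23 per group, as stated. The figure reproduces and does not depend on the present point. The endpoint it sizes is correction of anaemia, 95% against 60%.

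**2. The sections side by side.**

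| Place | Transferrin saturation after treatment? |
|---|---|
| 2.1 Methods | not scheduled |
| Project Summary | not among the iron-status tests |
| Data Analysis | not among the examples |
| 2.5 Laboratory Methods | assay described, no time points |
| 2.6.1 Outcome Measures | yes, before and after |
| 1.1.4.2 definition, as used in 2.6.1 | needed |

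**3. Direction.** Every woman with both SF and sTfR abnormal also has at least two of three abnormal, but not the reverse. A both-of-two rule therefore never counts more women as IDA than the three-marker rule.

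**4. Size (assumed inputs).** The documents give no marker positivity rates or correlations. Let p be the chance that each marker is abnormal in a woman who is still anaemic, B2 the chance that a given pair are both abnormal, and B3 the chance that all three are. Then:

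- P(at least 2 of 3) = 3·B2 - 2·B3
- P(both SF and sTfR) = B2
- share of IDA cases lost = 1 - B2/(3·B2 - 2·B3)

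With independent markers the loss is 1 - 1/(3-2p): 37.5% at p = 0.7, 28.6% at 0.8, 16.7% at 0.9, 9.1% at 0.95 and 0 at 1.

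With correlated markers (Gaussian copula, common correlation ρ):

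| p | ρ | 2 of 3 | both of 2 | share lost |
|---|---|---|---|---|
| 0.7 | 0.3 | 0.749 | 0.528 | 29.4% |
| 0.7 | 0.7 | 0.717 | 0.591 | 17.6% |
| 0.9 | 0.3 | 0.949 | 0.822 | 13.4% |
| 0.9 | 0.7 | 0.920 | 0.847 | 7.9% |
| 0.95 | 0.7 | 0.964 | 0.920 | 4.6% |
| 0.9 | 0.9 | 0.906 | 0.869 | 4.1% |

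For p of 0.7-0.9 and ρ of 0.3-0.7 the loss is about 8-30% of cases that still meet the three-marker rule. Full agreement of the markers gives 0.

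**5. Before/after comparison.** In an arm of 25 where no woman's iron status changes, all 25 still meet the three-marker rule. Under both-of-two, 25 × 0.079 = 2.0 to 25 × 0.294 = 7.4 of them would be scored as no longer having IDA.

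**6. Between arms.** Suppose correction were scored on the IDA rule, and take the planning rates as residual IDA of 5% and 40%. With the same share L lost in each arm, the contrast becomes 35 × (1-L):

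- L = 7.9%: residual 4.6% and 36.8%, contrast 32.2 points, down 2.8
- L = 29.4%: residual 3.5% and 28.2%, contrast 24.7 points, down 10.3

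As an outer case, independent markers with p = 0.7 turn 95% against 60% into 96.9% against 75.0%. Normal-approximation power at 23 per group then falls from 0.83 to 0.57; with p = 0.9 it is 0.73. If correction is judged on Hb alone, none of this applies.

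**The case against.** A reader might infer that the protocol judges IDA by a stricter rule after treatment than before, so that IDA falls artificially in every arm. The documents do not support that as a statement of fact. Three things in reply stand:

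- **The omission is not settled.** Section 2.1 does not say that only those three tests are done. Section 2.5 describes the saturation assay within the trial part of the protocol, and section 2.6.1 names saturation as a before/after outcome. This is a contradiction, not a decision to omit.
- **No section states a both-of-two rule.** The artificial fall needs saturation to go unmeasured, two abnormal markers still to be required, and some still-anaemic women to qualify only through saturation plus one other marker.
- **The 8-30% is not comparable with the planned 35 points.** It is a share of residual cases under chosen inputs, not percentage points of an arm. On the planning rates it amounts to roughly 3-10 points. Correction of anaemia in section 2.3 is not tied to the IDA definition, so the sized comparison may be untouched, as are the changes in Hb, SF and sTfR.

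It is also fair that one rule would apply in every arm. Where treatment does nothing, it produces no expected difference between arms.

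None of this removes the conflict. The only detailed visit schedule omits an input that the definition and the outcome list need, the Project Summary repeats the same short list, and the text offers no rule for classifying IDA without it.

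**Conclusion.** The point holds as an internal contradiction that leaves the follow-up IDA outcome undefined. Sections 2.1 and the Project Summary schedule Hb, SF and sTfR; sections 1.1.4.2 and 2.6.1 need transferrin saturation as well. If the schedule governs, the saturation outcome cannot be computed and the IDA definition cannot be carried forward unchanged.

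The bias is conditional. If two abnormal markers are still required, post-treatment IDA can only be understated. Within-arm improvement would then be exaggerated, including under placebo, and between-arm differences could be diluted but not created. The documents do not fix the size: it is about 8-30% of residual cases for assumed positivity of 70-90% and correlation of 0.3-0.7, less if the markers agree more closely, and zero if they agree fully. The effect on the 35-point contrast is roughly 3-10 points if correction is scored on the IDA rule with the same loss in both arms, and none if it is scored on Hb alone.

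**What to change.** Reconcile section 2.1 and the Project Summary with sections 2.5 and 2.6.1 before the first follow-up sample is taken, and state one IDA rule for all time points. Either route works:

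1. **Measure it.** Add serum iron and TIBC, by the method already in section 2.5, to the blood drawn at the end of intervention and at both later visits. The section 1.1.4.2 definition then applies unchanged throughout. The cost is one more assay on up to 125 × 3 = 375 samples.
2. **Drop it from the outcomes.** Score the IDA outcome from Hb, SF and sTfR at baseline and at follow-up alike, and delete transferrin saturation from section 2.6.1. This costs only wording. However, women who entered on saturation plus one other marker would not count as IDA at baseline on the outcome definition, so baseline prevalence in the randomised arms would fall below 100%.

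Under either route, section 2.3 should say whether correction of anaemia means Hb alone or the full IDA rule.
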